- Blood samples will be obtained pre-initial infusion of TK-112690/ placebo and 5, 24 and 48 hours post each initial infusion as well as on Day 1 of Week 6. Plasma will be obtained from the blood samples in order to determine surrogate markers of mucositis, e.g., CD40/CD40L, TNF- α , etc.
- Patients will be evaluated for extent and severity of mucositis using established mucositis rating scales, e.g., OMAS/Sonis, PROMS, WHO, and CTCAE/mucositis on the day prior to study start (Day 0), and 24 and 48 hours post each initial infusion of TK-112690/ placebo as well as on Day 1 of Week 6. Examination will assess the lining of the mouth, throat, and other linings of the digestive tract. Incidence of oral mucositis, duration of severe oral mucositis, throat soreness, severity of pain and use of parenteral or transdermal opioid analgesics will be assessed.

Study Population

Patients at least 18 years old, diagnosed with locally advanced or residual or recurrent or metastatic SCCHN and scheduled to receive 45 mg/m² MTX to treat their cancer. The diagnosis must be confirmed by histopathology or cytology.

Inclusion Criteria

- Male and female subjects over 18 years old with a histologically or cytological confirmed diagnosis of locally residual, recurrent or metastatic SCCHN.
- Subject must have failed at least onecourses of non-MTX chemotherapy, orone course of non-MTX chemotherapyand chemo radiation for treating their SCCHN.
- No prior systemic treatments for cancer (chemotherapy and/or radiotherapy) 4 weeks prior to screening.
- No other concurrent, active, invasive malignancies.
- An Eastern Cooperative Oncology Group (ECOG) performance status of 0 to 2.
- Must have a life expectancy of at least 6 months.
- History of brain metastases allowed if disease has stabilized or improved after radiation and/or craniotomy.
- No active angina or uncontrolled arrhythmia.
- No detectable infection including hepatitis B/C and HIV.
- Not pregnant or nursing. Women of childbearing potential must have a negative urine pregnancy

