- Subjects that have participated in any other investigative clinical trial in the past 4 weeks.

Dose and Dosing Regimen

The dose of METREXASSISTTM (TK-112690) will be 45 mg/kg administered parenterally over one hour in a clear, neutral, aqueous formulation (no organic chemical excipients). METREXASSISTTM will be given one hour before and 5 hours after the MTX treatment. The nutrient drink will be given one hour before METREXASSISTTM infusion. The MTX formulation will that traditionally used as standard-of-

care at a study site.

Test Product, Dose and Mode of Administration

- METREXASSISTTM (TK-112690 for Infusion) is a clear, sterile, neutral (pH=7.4), aqueous solution containing 5 mL of 100 mg/mL TK-112690.
- METREXASSISTTM is packaged as a 5 mL solution in a 10 mL flint glass vial with an elastomeric stopper held in place by an aluminum seal and flip-off cap. The concentration of TK-112690 in the solution is 100 mg/mL
- METREXASSISTTM will be administered as a continuous iv infusion over a duration of one hour in a volume of 250 mL normal saline.
- The nutrient drink, Fortasyn Connect[™] / Souvenaid[™], is commercially available as a 125 mL, 125 kcal solution. The drink is administered orally.
- The placebo is isotonic saline.

Reference Therapy or Comparator

Placebo-Isotonic saline

Follow-up

[figure not shown]
Subjects need to return at Day 1 of Week 6, which is two weeks from the last dose of the study drug.

Statistical Methods

- Safety: AEs, vital signs, physical examination data and clinical laboratory data will be analyzed using descriptive statistics with safety outcomes for patients in a dose group pooled & compared with patients in other groups.
- Mucositis: Scale data from individual doses groups will be analyzed using descriptive statistics.
- Surrogate Markers: Plasma concentration data evaluated for individual doses groups using descriptive statistics as well as compared with Surrogate marker data from the completed Phase 1bstudy.

INTRODUCTION

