⁵⁹Ciralik, H., Effects of N-Acetylcysteine on MTX-induced small intestinal damage in rats. The Mount Sinai Journal of Medicine. 2006.73; 1086-1092.

support. Palifermin is thought to maintain mucosal barrier integrity by stimulating basal cell proliferation and differentiation in the oral epithelia^{60,61}

One reason mucositis has remained a significant problem and limitation for the use of chemotherapy has been the lack of insight into the pathogenesis of the disease. In January 2002, the Multinational Association of Supportive Care in Cancer and the International Society for Oral Oncology assembled an expert panel to set guidelines for the evaluation, prevention, and treatment of mucositis.^{3,4} From this meeting,² a five-step model emerged to explain the development and progress of mucositis:

Step 1: Initiation,Step 2: Up-regulation of "message,"Step 3: Signaling and amplification,Step 4: Ulceration and inflammation, andStep 5: Healing.

Using this model, arealistic animal model can be used to examine potential cytoprotectants for chemotherapeutic-induced mucositis.

TK-112690 Preliminary data demonstrating the potential of TK-112690 as a cytoprotectant against MTX induced mucositis was demonstrated at Tosk using a published weight model that mimics virtually all of the features of "natural" mucositis.⁶² In this model, GI toxicity is induced in C57BL/6 mice by pre-dosing with lipopolysaccharide (LPS) on Day 1 followed by MTX injections on Days 2 and 3.

[figure not shown]
Typical results using this model are provided in the following Figure.

⁶⁰Blijlevens, N and Sonis, S.T., Palifermin(recombinant keratinocyte growth factor-1): a pleiotropic growth factor with multiple biological activities in preventing chemotherapy and radiotherapy induced mucositis Annals of Oncology. 2007 18: 817-826.

⁶¹ Duncan, M and Grant, G, Review article: oral and gastrointestinal mucositis-causes and possible treatments. Aliment PharmacolTher 2003; 18: p.853-874.

⁶²deKoning, BAE, Contributions of mucosal immune cells to MTX-induced mucositis, International Immunology 2006, 18: 941-949.

Figure 1. Box plots showing prevention of weight loss by TK-112690 in a mouse model for MTX-induced mucositis

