1.3.2 IN VIVO

Uridine Increase in Mice Post-TK-112690.

CD-1 female mice (n=3/treatment group) were injected ip with a range of TK-112690 doses (0, 15, 30 and 60 mg/kg) and plasma from the animals analyzed for concentration of uridine. Plasma uridine and TK-112690 concentrations were determined by HPLC from plasma samples collected 0.08, 0.50, 1, 2, 4 or 12 hours post TK-112690 injection. The HPLC assay used 5-fluorouracil as the internal standard for both uridine and TK-112690.

Results from the study at the two time points where uridine and TK-112690 were greatest are provided in **Table 1** The concentration of endogenous plasma uridine determined by the HPLC method described in this report is approximately $0.5 \ \mu g/mL$.

Table 1. Mean plasma concentrations of TK-112690 and uridine for 0.08 and 0.5 time points

	Concentration (µg/mL)						
	15 mg/kg Dose		30 mg/kg Dose		60 mg/kg Dose		
	Mean	SD	Mean	SD	Mean	SD	
TK-112690	10.33	7.66	38.27	14.70	77.88	49.52	
Uridine	1.57	1.00	1.53	0.93	2.28	1.16	

As expected, plasma concentrations of TK-112690 increased with increasing doses of TK-112690 administered either by ip or continuous infusion, which expected to be elevated through UPase inhibition by TK-112690.

⁷⁸Galanos C, Freudenberg MA, Reutter W. Galactosamine-induced sensitization to the lethal effects of endotoxin.Proc. Natl. Acad. Sc. USA. 1979; 76: 5939-5943

⁷⁹ Rosenthal GJ, Lebetkin E, Thigpen JE, Wilson R, Tucker AN, Luster, MI. Characteristics of 2,3,7,8teterachlorodibenzo-P-dioxin Induced Endotoxin Hypersensitivity: Association with Hepatotoxicity.Toxicology. 1989; 251: 239-251

1. LPS/MTX Weight Loss Model (See Figure 1).

A published weight model⁸⁰ was employed to determine the ability of TK-112690 to protect against MTX-induced mucositis. Mice injected with MTX/LPS alone showed a severe, highly significant weight loss from day 5 to day 8 compared to animals treated only with saline. A significant reduction in MTX/LPS weight loss occurred in animals treated with 60 mg/kg TK-112690. In addition, dose ranging studies with TK-112690 in this model demonstrated that TK-112690 prevented MTX-induced weight loss at a dose as low as 15 mg/kg. The protection was dose-dependent.

2. Effect of TK-112690 on MTX-induced Intestinal Permeability of Iodixanol.

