1.5.2.14 Mucositis Status

Patients were evaluated for mucositis status on Day 0, pre-dose (Day 1), 24 hours (Day 1), 48 hours (Day 2), at equivalent times on 2, 3, and 4 weeks post-dose. The mucositis evaluation included four standard scales: CTCAE/mucositis, WHO/Oral Mucositis, PROMS, and OMAS/Sonis.

Data for the scales are provided below. In general, the mucositis experience experienced by the patients was low, and many low values were recorded by the Scales. Much higher values would be expected in patients dosed with methotrexate but with no TK-112690.

Figure 15. Bar chart showing mean score NCI mucositis scale for individual dosing intervals at 24 and 48 hours post 15, 30, 45 or 60 mg/kg dose of TK-112690. Analysis includes data from all patients evaluated.

[figure not shown]

Figure 16. Bar chart showing mean score WHO oral mucositis scale for individual dosing intervals at 24 and 48 hours post 15, 30, 45 or 60 mg/kg dose of TK-112690. Analysis includes data from all patients evaluated.

[figure not shown]
[figure not shown]

Figure 17. Bar chart showing mean score PROMS scale for individual dosing intervals at 24 and 48 hours post 15, 30, 45 or 60 mg/kg dose of TK-112690. Analysis includes data from all patients evaluated.

CONFIDENTIAL Tosk, Inc **Figure 18**. Bar chart showing mean OMAS mouth pain score for individual dosing intervals at 24 and 48 hours post 15, 30, 45 or 60 mg/kg dose of TK-112690. Analysis includes data from all patients evaluated.

[figure not shown]
[figure not shown]

Figure 19. Bar chart showing mean OMAS difficulty swallowing score for individual dosing intervals at 24 and 48 hours post 15, 30, 45 or 60 mg/kg dose of TK-112690. Analysis includes data from all patients evaluated.

The scores in the mucositis scale tests suggest that TK-11290 at doses of 45 and 60 mg/kg, bid, mitigated mucositis produced by a relatively high methotrexate dose of 45 mg/m².

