7.1.3. Days 1 and 2 (Weeks 1-4)

Patients will be hospitalized on Day 1 and observed until after the 25-hour evaluations and plasma sample collection are obtained. All subjects will undergo the following on Days 1 and 2 of Weeks 1-4:

- An in-house CBC, Kidney function test, Liver Function test to be performed within 24 hours of expected methotrexate dosing to verify patient Fit to receive methotrexate.
- The nutritional supplement is ingested 2 hours prior to initiation of the MTX treatment, one hour prior to the TK-112690/placebo infusion.
- TK-112690/placebo is administered as a one hour infusion pre-MTX and 5 hours post-MTX (±15mins window period).
- One hour after the initial infusion of TK-112690 or placebo, MTX will be administered by continuous infusion for one hour (±15mins window period).
- Physical examination, vital signs, weight, mucositis evaluation at 24 and 48 hours post the initialTK-112690/placebo infusion.
- 12-lead ECG at 24 hours post initial TK-112690/placebo infusion.
- Laboratory tests (hematology, chemistry, coagulation and urinalysis) 24 and 48 hours post initial TK-112690/placebo infusion.

- Plasma samples will be collected for surrogate marker measurements pre-dose of the nutraceutical and 5, 24 and 48 hours initial infusion of TK-112690 orplacebo.
- Mucositis assessments (Section 20.6, Appendix 6) at 24 and 48 hours post initial infusion TK-112690 or placebo.
- AEs to be recorded at 5, 24 and 48 hours post initial infusion of TK-112690 or placebo.
- ± 15 mins of window period is considered acceptable for schedule of events.

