10.1.1. Sample Size and Associated Power

The primary objective of this Phase 2a trial is to evaluate the pilot efficacy and the safety/tolerability of MetrexassistTM administered intravenously to subjects with cancer also receiving 45 mg/m² MTX. This is

an exploratory study and is may not be powered to demonstrate statistical significance. The sample size is based not on statistical calculations but on the outcome in the Phase 1b study where all patients received TK-112690 experienced relatively little mucositis. Without the TK-112690 considerably more mucositis is expected, perhaps enough to achieve statistical significance. At a minimum, sufficient data will be obtained to accurately power the next study with TK-112690 and MTX.

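### No observer-graded mucositis examination is scheduled between about days 2 and 8 after MTX doses 1–3, or days 2 and 14 after dose 4; PROMS recall fills only part of the gap

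*Combined protocol and SAP*

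**What the plan says.** Section 7.1.3 sets the on-treatment scoring: "Mucositis assessments (Section 20.6, Appendix 6) at 24 and 48 hours post initial infusion TK-112690 or placebo". Table 12 agrees, and the synopsis gives the full post-baseline list: "24 and 48 hours post each initial infusion of TK-112690/ placebo as well as on Day 1 of Week 6". There is a baseline score on Day 0 (Section 7.1.2) and one at early withdrawal (Section 8.2). The synopsis places the last visit: "Subjects need to return at Day 1 of Week 6, which is two weeks from the last dose of the study drug".

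The timing of MTX comes from Section 7.1.3: "One hour after the initial infusion of TK-112690 or placebo, MTX will be administered by continuous infusion for one hour". Table 12 puts the second study infusion at 6 hours, which its footnote equates to 5 hours after MTX, so MTX starts at about hour 1.

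The only time course of MTX injury in the documents is the sponsor's mouse model. Section 1.0 describes "pre-dosing with lipopolysaccharide (LPS) on Day 1 followed by MTX injections on Days 2 and 3", and Section 1.3.2 reports "severe, highly significant weight loss from day 5 to day 8".

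For Phase 1b, Section 1.5.2.14 says "In general, the mucositis experience experienced by the patients was low". Section 10.1.1 bases the sample size on that outcome and adds: "Without the TK-112690 considerably more mucositis is expected, perhaps enough to achieve statistical significance".

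**The concern.** The primary objective is a first placebo comparison of mucositis. If injury appears and heals between about day 2 and the next examination, OMAS, WHO and CTCAE will not record it in either arm. A small difference could then mean that the drug does little or that the scores were taken too early.

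The same ambiguity sits under the design rationale. Every Phase 1b patient received TK-112690, there was no control arm, and the charted scores are at 24 and 48 hours. Low values at those times are what a protective drug would give, and also what scoring before onset would give. Section 10.1.1 takes the first reading and expects this trial to supply what is needed to power the next one. The synopsis also plans to assess incidence of oral mucositis and duration of severe oral mucositis. Duration cannot be followed by examination across a gap of several days.

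**Working it through.** **The plan's own figure.** The sample size of 22 (11 per arm) comes with no alpha, power, effect size, SD or event rate, and Section 10.1.1 says it was not calculated. There is nothing to reproduce, so the check is arithmetic on the schedule.

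**Inputs.** Time zero is the start of the first study infusion each week. MTX starts at hour 1. Doses are on Days 1, 8, 15 and 22. Scores are at hours 24 and 48 of each weekly cycle and on Day 36 (Day 1 of Week 6).

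**Hours after MTX.** Scoring hour minus 1: 24 − 1 = 23 h (0.96 days) and 48 − 1 = 47 h (1.96 days). If MTX is counted from the end of the one-hour infusion, these become 22 h and 46 h.

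**Next examination.** After doses 1–3: 168 + 24 − 1 = 191 h (7.96 days). After dose 4: (36 − 22) × 24 − 1 = 335 h (13.96 days).

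| Dose | Scores after MTX | Next examination | Unexamined time |
|---|---|---|---|
| 1, 2, 3 | 23 h, 47 h | 191 h | 191 − 47 = 144 h of each 168 h cycle |
| 4 | 23 h, 47 h | 335 h | 335 − 47 = 288 h |

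The one-day dosing window in Section 5.3 moves the next examination after doses 1–3 to 167 h or 215 h (6.96 or 8.96 days).

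**Mouse interval.** From the first MTX injection: 5 − 2 = 3 to 8 − 2 = 6 days. From the second: 5 − 3 = 2 to 8 − 3 = 5 days. Scheduled scores within 72–144 h of any of the four doses: 0. Within 48–120 h: 0, although the 47 h score falls only one hour short of that range.

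**PROMS recall.** The second PROMS questionnaire in Appendix 6 asks about the past week.
- At the 24 h visit of Weeks 2–4 it reaches from 191 − 168 = 23 h to 191 h after the previous dose, days 0.96–7.96. Days 3–6 are covered for doses 1–3.
- At Week 6 it reaches from 335 − 168 = 167 h to 335 h after dose 4, days 6.96–13.96. Days 3–6 are missed.
- The separate mouth-pain line on the first form asks about the present only.

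**The case against.** A reader might infer that mucositis is seen only one and two days after each dose, on every scale. The documents do not support that. Scores in Weeks 2–4 also fall about 8 and 9 days after the previous dose, and Week 6 falls 14 days after the last, so persistent or cumulative mucositis would be recorded. PROMS recall covers days 3–6 after three of the four doses.

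Adverse events give another route. They are CTCAE-graded whatever the cause (Section 9.1.1), documented to 28 days after the last dose (Section 9.1.4), and recorded with start and resolution dates and severity (Section 9.3). This stands as partial cover. It depends on what patients report, and it is not scheduled scoring on the efficacy scales.

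Phase 1b also contains evidence the other way. Section 1.5.2.14 concludes that 45 and 60 mg/kg reduced mucositis, from charts at 24 and 48 hours, so the sponsor reports a dose-related difference visible at those times. It is therefore too strong to say that both arms must look mild, or that the low Phase 1b scores were a timing artefact. The charts are not available here to check, and there was no placebo arm. Phase 1b also scored before dosing and at weeks 5 and 8 (Section 1.5.2.1).

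The timing anchor is weak. The model combines LPS with MTX and reads out body weight rather than oral lesions, and Figure 1 reports the change from Day 1 to Day 8, which does not isolate onset. Carrying its timing to patients is an inference.

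Finally, the study is declared exploratory. That lowers the stakes, but an exploratory study still needs scores that can be interpreted.

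**Conclusion.** The gap is a fact of the schedule. For a patient dosed and seen on time, no OMAS, WHO or CTCAE examination falls between about 2 and 8 days after doses 1–3, or between about 2 and 14 days after dose 4. Only PROMS recall reaches into it, and for days 3–6 only after doses 1–3. The one time course in the documents lies almost wholly inside it.

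The consequence is less certain, because the documents do not say when MTX mucositis appears in patients. A reader might want to convert the gap into a percentage of effect lost or a sample-size multiplier. That would need the share of the difference visible at 24 and 48 hours, the share persisting to days 8–9, and an average over visits. The documents give neither share, and the plan specifies descriptive statistics without defining such an average.

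What can be concluded is that the Phase 1b scores do not separate protection from early scoring, and that repeating the schedule leaves a null result open to the same doubt. A cheap amendment is worthwhile.

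**What to change.** Amend Section 7.1.3, Table 12 and the statistical methods:

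1. Score all four scales at the existing pre-MTX check in Weeks 2–4, before that week's infusion. The check falls within 24 hours before MTX, so about days 6–7 after the previous dose. Phase 1b already lists a pre-dose score.
2. Add one PROMS form, including the eating-function item, about 4–6 days after each MTX dose, above all after dose 4. Use a paper form completed at home, or a telephone call with a numeric rating in place of the marked line.
3. Compare the arms on the worst score in each dose interval, attributing pre-MTX scores to the preceding dose. Report the Week 1 scores at 24 and 48 hours separately as early values.

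**Cost.** 3 × 22 = 66 extra scoring occasions and 4 × 22 = 88 short forms, with no new visit. Burden rises slightly, some home forms will be missing, and some patients may need help completing them.

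**What remains.** The observer-graded gap after doses 1–3 shrinks from 144 h to about 97–120 h (a pre-infusion check 144–167 h after the previous MTX, minus 47 h), so the pre-MTX score reaches only the late edge of the mouse interval. Those scales stay unscored from day 2 to day 14 after dose 4, which the protocol should state as a limitation.

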7.1.4. Follow-Up Evaluations

All patients will undergo the following on Day 1 of Week 6:

- Perform a physical examination and determine vital signs, weight, and AE assessment.
- Determine ECOG performance status.
- For females of childbearing age, a pregnancy test will be performed.
- Perform laboratory tests (hematology, chemistry, coagulation and urinalysis).
- Obtain a blood sample for surrogate marker evaluation.
- Disease (tumor) assessment by CT scanning will be performed.
- Mucositis assessment (Section 20.6, Appendix 6).

8.0. SELECTION AND WITHDRAWAL OF SUBJECTS

8.1. PREGNANCY

Subjects who become pregnant during the study should discontinue the study immediately. Subjects should be instructed to notify the PI if it is determined after completion of the study that they became pregnant during the treatment phase of the study.

Whenever possible, a pregnancy should be followed to term, any premature terminations reported, and the status of the mother and the child should be reported to Tosk after delivery.

8.2. SUBJECT WITHDRAWAL CRITERIA

A subject may voluntarily discontinue study participation at any time. At any time, the PI may also at his/her discretion discontinue a subject's study participation. Subjects may be withdrawn from this study for the following reasons:

- At the PI's discretion in situations where the subject is unable to comply, or complies poorly with the protocol.
- Disease progression and/or experiences intolerable toxicity.
- Major protocol violation.
- Lost to follow-up.
- If TK-112690/placebo treatment is delayed due to toxicity for more than 2 weeks.
- Inter-current event preventing administration of study medication for more than 2 weeks.
- Subject withdraws consent.
- Subject becomes pregnant.
- Subject starts any other chemotherapy agent or anti-cancer treatment other than study therapy for refractory solid tumor, e.g., radiation therapy.

• Death.

If there is an ongoing toxicity due to the study agent, subjects must be followed with appropriate medical management until resolution or stabilization, regardless of evidence of progressive disease.

The subject will be advised in the Informed Consent Forms that he/she has the right to withdraw from the study at any time without prejudice and may be withdrawn at the discretion of the PI or Tosk at any time. In the event that the subject drops out of the study or is withdrawn from the study, the withdrawal CRF should be completed. On the withdrawal page the PI should record the date of the withdrawal, the person who initiated withdrawal and the reason for withdrawal.

Reasonable effort should be made to contact any subject lost to follow-up during the course of the study in order to complete assessments and retrieve any outstanding data.

At the time of study withdrawal, following will be recorded for these premature removals:

- Update medical history including any additional cancer therapies, including starting date (immunotherapy, targeted therapy, radiation and surgical interventions) if known.
- Physical examination and determination of vital signs, weight and AEs.
- Laboratory tests (hematology, chemistry, coagulation and urinalysis).
- Mucositis assessment (Section 20.6, Appendix 6).

Subjects with an ongoing apparently drug-induced toxicity will continue to be seen at monthly intervals until the toxicity resolves or stabilizes to a level acceptable to the medical monitor and the PI. If the subject starts new cancer therapy, the relationship to study drug should be re-assessed.

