No relationship among dose, age, BMI, or ECOG and disposition is apparent. Male patients completed the trial at a higher rate (14 of 19) than female patients (2 of 6).

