3.1.2. DOSE MODIFICATIONS

[figure not shown]
Treatment will be withheld following grade 3 or 4 adverse events. Treatment may be restarted when the adverse events have recovered to \leq grade 2. Subjects in whom treatment is withheld for > 2 weeks will have treatment discontinued permanently.

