20.4. APPENDIX **4:** INFUSION REACTION CRITERIA

Epinephrine (1:1000) for subcutaneous injection, diphenhydramine (12.5 mg to 50 mg) for iv injection, and any other medications and resuscitation equipment for the emergency management of anaphylactic reactions must be available in the room where the infusions are being performed.

Section 1

The subject's study treatment must be discontinued *immediately* if a Grade 4 AE occurs during the infusion of TK-112690, and the subject must be withdrawn from the study. The subject's study treatment must be discontinued *immediately* if a Grade 3 AE occurs during the infusion of TK-112690 and should not be completed even if the subject recovers. Subsequent administration of TK-112690should be preceded by prophylactic premedication as outlined in Section 2. If another Grade 3 infusion reaction occurs during a subsequent treatment day, treatment will again be discontinued for the rest of that infusion. If the investigator wishes to continue treatment in this subject, there should be discussion with the medical monitor about the possibility of reduced infusion rates for subsequent infusions.

If Grade 1 or 2 AEs occur during infusion of TK-112690, the subject may complete the treatment at half the previous infusion rate (180 minutes or shorter based on the acceleration of the infusion allowed after the first dose). Subsequent administration of TK-112690 should be preceded with prophylactic treatment as outlined in Section 2. To assess the events, please refer to the NCI CTCAE in the Study Reference Manual.

Treatment Recommendations Prior to, During, and Immediately After Infusion Section 2 Prophylactic Treatment Prior to Infusion

Prophylactic measures prior to the administration of should not be initiated unless a previous infusion reaction has occurred. Subjects who have previously experienced a reaction to must receive prophylactic treatment prior to subsequent infusions. Prophylactic treatment with acetaminophen (1 g) and diphenhydramine HCl (12.5 to 50 mg; or equivalent dose of a similar agent) by mouth 30 to 60 minutes prior to the start of the infusion is recommended. **Steroids should not be used as pre-medication in this study**.

Section 3 Treatment of Infusion Reactions

The use of acetaminophen plus an antihistamine, such as diphenhydramine (or similar agent), is recommended for the treatment of an infusion reaction. For adjustment to the subject's infusion see Section 1.

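### Stopping study treatment is not separated from leaving the study, so scheduled mucositis scores can be lost after a patient stops for toxicity

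*Combined protocol and SAP*

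**What the plan says.** The documents give three rules on stopping:

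- **Section 3.1.2** deals with treatment alone: "Subjects in whom treatment is withheld for > 2 weeks will have treatment discontinued permanently".
- **Section 8.2** deals with the study. Its list opens "Subjects may be withdrawn from this study for the following reasons" and includes "If TK-112690/placebo treatment is delayed due to toxicity for more than 2 weeks", "Disease progression and/or experiences intolerable toxicity", and an intercurrent event that prevents dosing for more than 2 weeks.
- **Appendix 4, Section 1** is mandatory. After a Grade 4 event during the infusion, treatment stops at once and "the subject must be withdrawn from the study".

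At withdrawal, Section 8.2 asks for one assessment: history update, physical examination, vital signs, weight, adverse events, laboratory tests and mucositis. ECG, ECOG status, a marker sample and CT are not on that list.

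Section 7.1.3 and Table 12 set the Weeks 1-4 mucositis scores at 24 and 48 hours after each week's initial infusion. For Week 6, Section 7.1.4 says "All patients will undergo the following on Day 1 of Week 6", and Section 5.2 is worded in the same way. Neither says whether a withdrawn patient is included.

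Section 8.2 ties its own later follow-up to attribution: "Subjects with an ongoing apparently drug-induced toxicity will continue to be seen at monthly intervals". Sections 9.1.4 and 9.3 and Appendix 5 contain further adverse-event follow-up that does not depend on attribution.

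**The concern.** One event, a toxicity hold of more than 2 weeks, ends treatment in one section and may end study participation in another. Sites can read this differently. A site that follows 8.2 or Appendix 4 has no instruction to keep scoring mucositis after the withdrawal assessment.

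The outcome can also contribute to its own missingness. Mucositis is the efficacy measure for the primary objective (Sections 2.1 and 3.1). Under the CTCAE scale in Appendix 6, Grade 3 mucositis means severe pain that affects eating and drinking. Section 3.1.2 withholds treatment for any Grade 3 or 4 event, and Section 8.2 allows withdrawal when the resulting delay is long enough. The patients with the worst scores may therefore be the ones whose later scores are missing.

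The synopsis also promises the duration of severe oral mucositis, which cannot be observed once scoring stops. Section 10.4 offers no remedy: it tabulates patients lost to follow-up and has no rule for withdrawn patients.

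**Working it through.** The plan states no figure to reproduce. Section 10.1.1 says the sample size does not come from a statistical calculation, and no dropout rate is given. The check is a count of assessments, a check of when each rule can act, and a rate carried over from Phase 1b.

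**1. Mucositis assessments at stake** (Table 12, Sections 7.1.2 to 7.1.4)

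Scheduled: Day 0, two in each of Weeks 1-4, and Week 6, so 1 + 4 × 2 + 1 = 10. A patient who leaves after Week *w* has 1 + 2*w* of them.

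| Leaves after | Obtained | Lost | Lost if Week 6 is kept |
|---|---|---|---|
| Week 1 | 3 | 7 | 6 |
| Week 2 | 5 | 5 | 4 |
| Week 3 | 7 | 3 | 2 |

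Each loss is offset by one withdrawal score.

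**2. When each rule can act**

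Planned dosing days are 1, 8, 15 and 22. If the Week 2 dose is the first one withheld, a delay of more than 14 days is not reached until after Day 8 + 14 = Day 22, the planned Week 4 dosing day. The 2-week trigger therefore cannot remove a patient before about Week 4. In that patient the Week 2 and Week 3 scores (4 of them) are already missing because no infusion was given. Withdrawal then puts at risk the Week 4 pair and the Week 6 score. Intolerable toxicity, progression and a Grade 4 event during infusion can act from the first week. There are thus two gaps: the withdrawal wording, and visits that exist only relative to an infusion.

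**3. What is kept for safety**

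- Section 9.1.4: all adverse events are documented for 28 days after the last dose. Events that are serious, life-threatening or related are followed beyond that.
- Section 9.3: adverse events are monitored to resolution or, if chronic, until a cause is identified.
- Section 9.1.5: unexplained abnormal laboratory values are repeated.
- Appendix 5: serious events within 28 days are reported whatever the attribution.

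For a patient last dosed on Day 1, the 28 days end on Day 29. Day 1 of Week 6 is Day 36, so the documentation window falls one week short of that visit. What can be lost is the scheduled laboratory tests, examinations, vital signs, ECGs and marker samples, plus the Week 6 ECOG and CT if that visit is not done.

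**4. How many patients** (Section 1.5.2, Phase 1b)

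- Discontinued for adverse events: 4/25 = 16% (exact 95% CI 5% to 36%). Applied to 22 patients: 0.16 × 22 = 3.5.
- Not completing for any reason: 25 − (14 + 2) = 9, and 9/25 = 36% (exact 95% CI 18% to 57%). Applied to 22: 0.36 × 22 = 7.9, with a range of about 4 to 13.

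Only the first rate relates to stopping for toxicity. The second includes patients whom no rule could retain.

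**The case against.** The strongest reply is that the protocol already covers most of this. Section 8.2 is permissive, and only the Grade 4 infusion rule is mandatory. Mucositis is scored at withdrawal, Week 6 is worded for all patients, and adverse events are followed in several places regardless of attribution. The four Phase 1b discontinuations for adverse events were all anemia, not mucositis. The trial is an exploratory pilot with descriptive analysis of the scales.

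Much of that stands and limits the point. A reader might infer from 8.2 that every patient with severe toxicity must leave the study and loses safety follow-up. The permissive wording and the provisions in 9.1.4, 9.3 and Appendix 5 do not support this. A reader might also reason that, because every Phase 1b event was judged unrelated to TK-112690, nobody would have been followed. That holds only for the attribution-based follow-up in 8.2, not for the protocol as a whole.

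The reply does not remove the gap in mucositis scoring. Discretion lets sites differ, one withdrawal score does not replace a series, and the Week 6 wording does not say whether it overrides withdrawal. A descriptive pilot meant to supply data for powering the next study (Section 10.1.1) still depends on scores that are not selectively missing.

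**Conclusion.** The point holds as a conflict of wording with a consequence for the primary outcome. Sections 3.1.2, 5.2, 7.1.4, 8.2 and Appendix 4 do not distinguish a patient off treatment from a patient out of the study, and the remaining infusion-timed mucositis scores are not provided for after treatment stops. An early leaver loses between 3 and 7 of 10 scheduled scores, depending on the week and counting Week 6 as lost, less one withdrawal score. If the Phase 1b adverse-event discontinuation rate carried over, which is an assumption from a small study without a placebo arm, about 3 to 4 of 22 patients would be affected.

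Two stronger readings are tempting. One is that about 8 of 22 patients would be lost through this rule; that figure rests on all-cause non-completion. The other is that placebo patients would stop more often and the arms would be pulled together. Nothing in the documents shows which arm would stop more often, and neither the direction nor the size of any bias can be computed. The supportable statement is that the missing scores may be informative.

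**What to change.** Reconcile Sections 3.1.2, 5.2, 7.1.4, 8.2 and Appendix 4 as follows:

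- Define discontinued from study treatment separately from withdrawn from the study. Reserve the second for consent withdrawn, loss to follow-up and death. Assign each remaining reason in 8.2 (for example protocol violation, poor compliance, pregnancy) explicitly to one of the two.
- Keep treatment discontinuers on the scheduled mucositis and safety assessments through Week 6 unless they withdraw consent, whatever the attribution of the event.
- When no infusion is given, anchor the weekly assessments to the planned study day.
- State in 5.2 and 7.1.4 that Week 6 includes patients who have stopped treatment.

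The rules for when treatment stops are not changed. Collecting the scores does not by itself bring them into the analysis: Section 10.2.1 still restricts the efficacy population to patients with at least four doses, so the use of these scores should be stated there.

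The cost is wording in the protocol, consent form and CRF, and a few already scheduled visits for patients off treatment. Some will decline.
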